1.7.1 Vertical and Horizontal Transmission

ST-920 employs a replication defective AAV vector and persistence in bodily fluids is not anticipated past 60 days based on animal data. No data are available suggesting transmission of the AAV vector to the offspring of an exposed male subject. As a precaution to avoid transmission to partners of the viral vectors, through shedding, male subjects must agree to use a highly effective form of contraception (e.g., true sexual abstinence, documented vasectomy, condom) and refrain from sperm donation from the time of ST-920 administration until a minimum of 3 consecutive semen samples are negative for AAV2/6 after administration of ST-920 and a minimum of 90 days after ST-920 administration. Female subjects must agree to use a highly effective form of contraception (described in Inclusion Criteria 9), and they must refrain from egg donation from the time of ST-920 administration until all the samples are negative for AAV2/6 after administration of ST-920.

ST-920 vector shedding has been shown in animal and human studies and is generally cleared in bodily fluids by 2 months post dose administration. Results from the first six subjects of ST-920-201 show that the AAV6 vector is not detectable after 2-8 weeks post-dosing. To mitigate any potential risks to other individuals or the environment from vector shedding, subjects are instructed to avoid the contact of their body fluids or excrements with other individuals or the environment, and maintain hygiene and cleanliness of their hands and the environment within an appropriate time period after receiving treatment; items to be disposed after coming in contact with the body fluids or excrements of subjects should be sealed in disposable garbage bags. For details, refer to the Laboratory Manual.

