Inclusion & Exclusion Criteria	
Inclusion Criteria
 
 ≥ 18 years of age Signed, written informed consent Diagnosis of Fabry disease One or more of the following symptoms: i) cornea verticillata, ii) acroparesthesia, iii) anhidrosis, iv) angiokeratoma Subjects who are on ERT or are ERT-naïve or are ERT-pseudo-naïve (defined as not having received ERT treatment during the 6 months prior to baseline). For subjects receiving ERT, ERT must have been administered at a stable dose and regimen for at least 6 months (defined as not having missed more than 3 doses of ERT during the 6 months prior to consent). Subjects on migalastat (Galafold™) must agree to withdraw migalastat prior to Baseline and, if non-responder to migalastat (based on clinical and/or biochemical assessments), undergo an incisional skin biopsy and kidney biopsy. Male subjects must refrain from sperm donation from the time of ST-920 administration until a minimum of 3 consecutive semen samples are negative for AAV2/6 after administration of ST-920 and a minimum of 90 days after ST-920 administration. Female subjects must refrain from egg donation from the time of ST-920 administration until all the samples are negative for AAV2/6 after administration of ST-920. Subjects must agree to use a highly effective form of contraception from the time of ST-920 administration until a minimum of 90 days after ST-920 administration and, for male subjects, a minimum of 3 consecutive semen samples are negative for AAV2/6 after administration of ST-920. Highly effective birth control methods include: 
 a documented vasectomy or permanent sterilization 	

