1.7 Benefit-Risk Assessment and Study Hypothesis

Fabry disease is an inherited lysosomal storage disorder that results from mutations in the gene encoding the enzyme α -Gal A. Decreased levels of α -Gal A result in the accumulation of toxic levels of a type of glycosphingolipid, Gb3, in the blood vessels and body tissues. The severity of the symptoms varies among individuals depending upon their specific *GLA* mutation and the level of residual α -Gal A activity. Currently, the treatment of choice for this patient population is ERT using recombinant α -Gal A or chaperone therapy.

The objective of ST-920 investigational therapy is to provide patients with Fabry disease stable therapeutic, liver-specific expression of α -Gal A which may improve on the current clinical outcomes of ERT therapy and ultimately replace ERT altogether.

The potential risks of ST-920 include insertion mutagenesis (carcinogenicity), vertical and horizontal transmission and off-target effects.

Mitigation strategies are in place for each potential risk and are described in the Investigator Brochure. Additional risks and related mitigation strategies are listed below.

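### The male contraception rule is meant to keep shed vector from partners, but Section 1.7.1 and inclusion criterion 9 accept vasectomy alone, which does not prevent semen contact

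*Combined protocol and SAP*

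**What the plan says.** Section 1.7.1 (Vertical and Horizontal Transmission) gives the purpose of the male rule: "As a precaution to avoid transmission to partners of the viral vectors, through shedding". In the same sentence it offers men three examples of an acceptable method, abstinence, vasectomy and condom, as alternatives: "viral vectors, through shedding, male subjects must agree to use a highly effective form of contraception (e.g., true sexual abstinence, documented vasectomy, condom". The rule runs from dosing until three successive semen samples are negative and at least 90 days have passed.

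Inclusion criterion 9 (Section 4.1 and the synopsis) turns this into an eligibility condition. It asks for one highly effective method. Its first item is "a documented vasectomy or permanent sterilization"; condom is a separate second item. Combined hormonal, progestogen-only, intrauterine device and intrauterine hormone-releasing methods follow, then true abstinence. None is limited to one sex.

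The next paragraph of 1.7.1 adds a safeguard for everyone: "subjects are instructed to avoid the contact of their body fluids or excrements with other individuals or the environment". The sentence goes on to hygiene, "within an appropriate time period after receiving treatment", and the paragraph ends "For details, refer to the Laboratory Manual". Section 1.7 says of the risks it lists: "Mitigation strategies are in place for each potential risk and are described in the Investigator Brochure".

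**The concern.** A rule should be able to do what it is said to be for. This one is introduced as protection of partners from vector in semen, and its end depends on semen tests. One of its three named methods, vasectomy, prevents conception without preventing contact with semen. A site applying criterion 9 as written could correctly tell a vasectomised man that he complies and needs no barrier, including in the first weeks after dosing, when shedding is most likely.

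The person affected is a partner who has not enrolled. Sections 1.7 and 8 both list horizontal and vertical transmission as potential risks of ST-920. This is a matter of safety wording; sample size, error rates and analyses are untouched.

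**Working it through.** No figure in the plan bears on this point, so the check sets the texts side by side.

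**Step 1: does the protocol treat semen as a route?** Yes. The male rule in 1.7.1 and criteria 7 and 9 all wait for negative semen samples, and Section 6.2.10 includes semen among the specimens tested for vector genomes.

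**Step 2: which accepted methods prevent semen contact?**

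| Method | Named for men in 1.7.1 | Listed in criterion 9 | Prevents semen contact |
|---|---|---|---|
| True abstinence | yes | yes | yes |
| Condom | yes | yes | yes |
| Vasectomy or permanent sterilisation | yes (vasectomy) | yes | no |
| Combined hormonal | no | yes | no |
| Progestogen-only hormonal | no | yes | no |
| Intrauterine device | no | yes | no |
| Intrauterine hormone-releasing system | no | yes | no |

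In 1.7.1, 2 of 3 named methods serve the stated purpose and 3 − 2 = 1 does not. In criterion 9, 2 of 7 do and 7 − 2 = 5 do not. The four hormonal and intrauterine items matter here only if a man may rely on his partner's method. Criterion 9 does not rule that out.

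**Step 3: does anything else require a barrier?** Neither 1.7.1, criterion 9 nor the synopsis asks a vasectomised man to add a condom. The general instruction in 1.7.1 would cover semen if followed, since semen is a body fluid. It does not mention semen, intercourse or condoms, and it does not alter the list of accepted methods.

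**Step 4: do the data settle the early weeks?**

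- Human: "Results from the first six subjects of ST-920-201 show that the AAV6 vector is not detectable after 2-8 weeks post-dosing". The statement does not say which sample types it covers, so it gives no semen result.
- Mouse, ST-920 (Section 1.3.2): semen had no measurable vector at 3 months, about when the 90-day minimum ends. This says nothing on the first weeks.
- SB-913, a product with the same capsid proteins (Section 1.3.2): no vector in semen, but no sampling time is given.
- Monkey (Section 1.3.2): the shedding results described are for saliva, urine and feces.

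The semen evidence is reassuring as far as it goes. It does not show that semen is free of vector in the weeks just after dosing.

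**The case against.** The strongest reply is that the same section already handles the risk. Its second paragraph is expressly about risk to others from shedding, and unprotected intercourse by a vasectomised man would breach the instruction to avoid body-fluid contact. The open-ended period is no answer to this. The phrase may qualify only the hygiene clause, and even if it qualifies both, an undefined end leaves no gap in the first weeks. This part stands: if the instruction is followed, the early weeks are covered.

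Second, Section 1.7.1 deals with vertical as well as horizontal transmission, and vasectomy is a sound method for preventing conception. Criterion 9 states no partner-shedding purpose of its own. This also stands, but the sentence in 1.7.1 that sets the male rule names partners and shedding, and criterion 9 applies the rule.

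Third, the Laboratory Manual and Investigator Brochure are not part of the public documents, and the consent pages were removed. Any of them may already tell men to use condoms. That limits how firmly one can call protection absent. It does not repair the criterion, which a site will read on its own.

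Fourth, once semen is clear, a barrier up to day 90 may be more than shedding requires. That is arguable, but 90 days is the protocol's own minimum for all male subjects, and keeping it avoids a separate rule for vasectomised men.

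A reader might infer that partners of vasectomised men are exposed to vector for 2 to 8 weeks. The documents do not support that: it assumes semen follows a human result whose sample type is not stated, and the reported animal semen results are negative.

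**Conclusion.** The mismatch is real. The rule in 1.7.1 has a stated purpose that one of its three named methods cannot serve, and criterion 9 carries the same gap into eligibility. The general instruction covers it only in part, because it leaves the accepted methods as they are.

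The size is unknown and probably small. The documents give no human semen-specific result and no count of vasectomised men. They describe a replication-defective vector, with lot release requiring a negative test for replication-competent virus (the second section numbered 1.7.13). It would go too far to infer that the protocol ignores partner exposure or leaves partners wholly unprotected.

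The conclusion rests on two assumptions: that vasectomy does not prevent contact with ejaculate, and that the manuals and consent form do not already impose a barrier. If they do, the change only brings the criterion into line. It is a worthwhile, inexpensive improvement to safety wording.

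**What to change.** In Section 1.7.1, criterion 9 of Section 4.1 and the synopsis, state that all male subjects, including vasectomised men and men whose partners use a hormonal or intrauterine method, must use a condom or practise true abstinence. Keep the existing period: until three successive post-dose semen samples are negative and at least 90 days have passed since dosing.

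The cost is a protocol amendment with matching consent wording, and re-consent where Section 5 requires it. Vasectomised men, and any man relying on a partner's method, take on a temporary restriction of at least 90 days. No visit, sample or analysis is added.

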1.7.2 Off-Target Effects

Because the viral vector construct includes a liver-specific promoter for the *GLA* gene and liver-specific enhancers, the transgene should only be expressed in the liver, thus limiting the risk of off-target effects to the liver. Off-target effects from circulating enzyme are not anticipated, as supraphysiological levels of produced enzymes in animal preclinical experiments did not reveal any relevant adverse effects. Despite this, subjects will be followed for a total of 52 weeks (-2 weeks/+ 1 month) post-ST-920 infusion in this study. Subjects will also be encouraged to participate in an additional, optional separate long-term follow-up study (of 4 years) for a total of up to 5 years from infusion to facilitate detection of potential delayed AEs associated with ST-920 treatment.

1.7.3 Humoral Immune Response to AAV

As described in [Section 1.3.3](#) of this protocol, in the GLP C57BL/6 mouse studies, the no-observed-adverse-effect level (NOAEL) was $\geq 1.50\text{E}+14$ vg/kg, the highest dose tested. In the GLP monkey study, ST-920PC-related findings were limited to animals that did not receive an immunosuppression treatment ($6.00\text{E}+13$ vg/kg). There were no adverse findings related to a single IV administration of ST-920PC up to $5.00\text{E}+13$ vg/kg, the highest dose level tested, hence risk mitigation strategies are not needed.

Patients treated with ST-920 are expected to develop a humoral antibody response against the AAV capsid. An enzyme-linked immunosorbent assay has been developed to detect anti-AAV6 total antibodies from patient serum post-dose throughout the study. This anti-AAV6 antibody assay has been validated and sample analysis will follow FDA and EMA recommended tiered immunogenicity testing approach to confirm a positive response.

1.7.4 Development of Neutralising Anti-Human α -Gal A Antibodies

Subjects treated with ST-920 carry a similar risk of developing an antibody response to the treatment as with other biologic interventional therapies. Two validated assays following FDA and EMA guidelines on immunogenicity assessment, total antibody and neutralizing antibody assays, are in place to assess and monitor treatment-elicited antibody response to transgene expressed α -Gal A.

1.7.5 Vector-induced Hepatitis and Loss of α -Gal A Expression

As described in [Section 1.4](#) of this protocol, based on Sangamo's prior clinical experience with AAV2/6 vector, an ALT elevation (suggestive of an immune reaction to the viral capsid) may be observed. Subjects will be closely monitored for ALT elevation throughout the study and the protocol-defined treatment (or treatment at the discretion of the Investigator and agreed upon with the Medical Monitor) with corticosteroids may be initiated in response. Corticosteroid dose selection and guidance are provided in [Appendix 3](#).

1.7.6 Transduction of Extra-Hepatic Tissues

As stated in the Investigator Brochure, ST-920 includes a liver-specific promoter for the *GLA* gene and liver-specific enhancers, therefore, the transgene should only be expressed in the liver, thus limiting the risk of off-target effects. Off-target effects were not observed in nonclinical studies where supraphysiological concentrations of produced enzyme were attained. Subjects will be closely followed for up to 5 years after ST-920 administration, with standard safety monitoring, described in [Protocol ST-920-LT01](#), [Appendix A](#), [Schedule of Events](#).

1.7.7 Corticosteroids to Suppress Immune Hepatitis

Based on Sangamo's prior clinical experience with AAV2/6 vector, it is possible that an ALT elevation (suggestive of an immune reaction to the viral capsid) may be observed. Subjects will be closely monitored for ALT elevation throughout the study and the protocol-defined treatment (or treatment at the discretion of the Investigator and agreed upon with the Medical Monitor) with corticosteroids may be initiated in response. The corticosteroid dosing regimen and tapering schedule are provided in [Appendix 3](#).

1.7.8 Insertional Mutagenesis and/or Tumorigenesis

The consensus in the gene therapy field is that insertional mutagenesis and carcinogenic risks associated with AAV gene therapy vectors is low. AAV vectors predominantly persist as episomal structures and integration frequency of AAV is estimated to be very low. There are no attributes of ST-920 that indicate that this AAV6 vector has unique properties that increase

oncogenic risk. ST-920 hGLA expression is driven by a liver specific promoter/enhancer and lacks the strong viral promoters which are associated with increased carcinogenicity risk. While insertional mutagenic risk cannot be completely excluded, the overall weight of the evidence indicates the risk is low.

The balance between benefit and (theoretical) risk should be weighed, and long-term monitoring for potential hepatocellular carcinogenicity will be key. The clinical plan includes monitoring for hepatocellular carcinoma (HCC)/liver masses by magnetic resonance imaging (MRI) or equivalent imaging modality at 24 weeks and at 1 year post ST-920 administration. In addition, the long-term safety of ST-920 will be evaluated as part of the long-term follow-up (LTFU, 4 years) study for 5 years from ST-920 infusion. This will include serial alpha fetoprotein (AFP) testing and liver imaging to monitor for potential liver masses at Months 12, 24, 36, and 48 (\pm 2 months).

1.7.9 Exposure to Supraphysiological Levels of α -Gal A

Nonclinical studies administered ST-920 IV to mice at doses up to $1.50\text{E}+14$ vg/kg and assessed plasma α -Gal A activity over 3 months. Plasma α -Gal A activity increased in a dose-dependent manner in mice treated with ST-920 and remained stable over the 3-month study duration. Overall, supraphysiological levels of α -Gal A activity (up to $\sim 4,100$ -fold in male and $\sim 2,200$ in female mice at 3 months) were observed in plasma, compared to those in vehicle control group. No ST-920 treatment-related adverse effects were seen and the NOAEL was considered to be $\geq 1.50\text{E}+14$ vg/kg, the highest dose tested. These results support safety of supraphysiological levels of plasma α -Gal A activity.

1.7.10 Risks of Kidney Biopsy

For subjects who are ERT-naïve or ERT-pseudo-naïve (defined as not having received ERT treatment during the 6 months prior to baseline) and selected subjects previously on migalastat who the Principal Investigator, in conversation with the Sponsor Medical Monitor, considers a non-responder to migalastat based on clinical and/or biochemical assessments, a kidney biopsy will be performed at baseline and after 6 months of dosing. The risks associated with this procedure include bleeding and infection. The bleeding is usually minor but can be severe in rare cases, requiring surgery to stop the bleeding. Management will be based on local guidelines. Infection will be treated based on standard of care. There is a low risk of puncturing adjacent organs; to reduce this risk, the procedure is guided by ultrasound. Local anesthesia and pain medication during and after the procedure will be based on local guidelines, considering potential risks of adverse reactions to such medications.

1.7.11 Risks of Skin Biopsy

Skin biopsy will be performed using incisional or punch biopsy techniques. All biopsies will result in a scar. Some scars may be raised, which is more likely if the biopsy is taken on the upper body. Scars fade gradually. The biopsy will be done in non-exposed areas of the skin such as the abdomen.

1.7.11.1 Risks of Incisional Skin Biopsy

Incisional skin biopsy may produce discomfort, which will be mitigated by local anesthesia. A minor burning sensation may occur when the freezing is injected, but usually subsides in a few seconds. Skin biopsies may also be associated with bleeding, which will be managed by applying pressure and a bandage. Complete healing of the wound may take weeks.

In addition to these risks of bleeding and scarring, there can be bruising, infection, and an allergic reaction to topical antibiotics. These risks will be mitigated by keeping the area clean and covering the site with a breathable bandage.

1.7.11.2 Risks of Punch Biopsy

Punch skin biopsy may produce discomfort, which will be mitigated by local anesthesia. A minor burning sensation may occur when the freezing is injected, but usually subsides in a few seconds. Skin biopsies may also be associated with bleeding, which will be managed by applying pressure and a bandage. Complete healing of the wound may take weeks.

In addition to these risks of bleeding and scarring, there can be bruising, infection, and an allergic reaction to topical antibiotics. These risks will be mitigated by keeping the area clean and covering the site with a breathable bandage.

1.7.12 Risks of Liver Biopsy

Liver biopsy will be required in the presence of a liver mass > 2 cm and elevated AFP (described in [Section 6.2.8](#)). The bleeding is usually minor but can be severe in rare cases, requiring surgery to stop the bleeding. Management will be based on local guidelines. Infection will be treated based on standard of care. There is a low risk of puncturing adjacent organs; to reduce this risk, the procedure is guided by ultrasound. Local anesthesia and pain medication during and after the procedure will be based on local guidelines, considering potential risks of adverse reactions to such medications.

1.7.13 Risks Associated with DNA Impurities

To control for residual host cell DNA in the Sangamo gene therapy manufacturing process, benzonase is added to the cell harvest prior to purification as a mitigation strategy to prevent residual DNA being larger than 200 base pairs. The benzonase enzyme digests all forms of nucleic acid by hydrolyzing with high efficiency (nearly 99.95%) unencapsidated nucleic acid oligomers into smaller nucleotide fragments of <10 base pairs in length. Due to high efficiency of benzonase treatment, there is a high probability that the total amount of residual host cell DNA observed is within the expected size range, thus posing no concern based on current regulatory guidance. Finally, Sangamo is characterizing potentially encapsidated DNA with both short and long read next generation sequencing for any nucleotides greater than 200 base pairs and to date has not found any unexpected areas of concern. All DNA sequences detected are process related and found in extremely low percentages of total encapsidated nucleic acids.

1.7.13 Risks Associated with Replication Competent AAV

ST-920 employs a replication defective AAV vector and persistence in bodily fluids is not anticipated past 60 days based on animal data. The risk associated with the generation of a replication competent AAV in the manufacturing process is very low, based on the presence of engineering and analytical controls that are implemented during the manufacture and release of the ST-920 drug product. The manufacturing process is designed to make use of two separate baculovirus infected insect cells (BIICs), namely Helper and Vector BIICs. The Helper BIIC contains a plasmid that provides rep/cap genes while Vector BIIC contains a plasmid that provides ITR, transgene and regulatory elements. This strategy allows for separating the ITR region from rep/cap elements thereby de-risking the possibility of producing a replication competent AAV during the manufacture of the ST-920 drug product. In addition, the control strategy includes a lot release test for the detection of a replication competent AAV. A negative test result for this assay is required for the lot release, confirming that the AAV drug product is replication deficient.

